9.4 EXPLORATORY

Blood and, if possible, BAL, tracheal aspirate, or sputum (induced or expectorated) will be collected to investigate the following exploratory questions:

10 SUPPORTING DOCUMENTATION AND PROCEDURES

10.1 INFORMED CONSENT PROCESS

The Investigator at each investigational site is responsible for ensuring that informed consent for study participation is given by each patient or their legal representative prior to collection of study data and administration of the study product. The Investigator will not undertake any intervention specifically required only for the clinical study until valid consent has been obtained. If consent has not been obtained, a patient cannot be enrolled into the study.

Consent will be sought directly from patients if possible. However, given that most patients in ICU will not be able to give written informed consent themselves due to alteration in their level of consciousness caused by therapeutic sedation, informed consent will be sought from a qualified representative. Consent can be obtained electronically if applicable.

If a protocol amendment is required, the informed consent form (ICF) may need to be revised to reflect those changes. If the ICF is revised, it must be reviewed and approved by the appropriate ethics committee and signed by all patients (or their representatives) subsequently enrolled in the study as well as those currently enrolled in the study.

10.2 STUDY DISCONTINUATION AND CLOSURE

Premature termination of the clinical trial may occur because of a regulatory authority decision, change in opinion of the IRB or medical monitor. Additionally, recruitment may be stopped for reasons of particularly low recruitment, protocol violations, or inadequate data recording. Specifically, the study will be stopped if:

- study Sponsor or a regulatory body decides for any reason that subject safety may be compromised by continuing the study; or
- the Sponsor decides to discontinue the development of the intervention to be used in this study.

10.3 MEDICAL MONITOR

The medical monitor will be a Sponsor physician or Sponsor-appointed physician with appropriate experience to oversee study conduct on the Sponsor's behalf, consult with site investigators, review and synthesize safety information from the various clinical sites, and to apply study-stopping criteria. All decisions by the medical monitor affecting study conduct, including the application of study-stopping or dose-escalation rules, will be documented in the study record.

10.4 RECORDING OF PROTOCOL DEVIATION

If the impact of the protocol deviation disrupts the study design, may affect the outcome (objectives), or compromises the safety and welfare of the subjects, the deviation must be reported to the medical monitor within three business days. Include the following information on the Sponsor-supplied exception/deviation form: protocol number, subject study number, description of the exception/deviation from protocol and rationale. Ensure all completed exception/deviation forms are signed by the Site Investigator and submitted to the Study Sponsor and medical monitor for review. Once approval of the exception request or acknowledgment of the deviation has been granted by the Sponsor and medical monitor, the exception or deviation will be submitted to IRB and all other applicable committees.

10.5 DATA HANDLING AND RECORD KEEPING

Study documents should be retained for a minimum of 2 years after the last approval of a marketing application in an International Conference on Harmonization (ICH) region and until there are no pending or contemplated marketing applications in an ICH region or until at least 2 years have elapsed since the formal discontinuation of clinical development of the study intervention. These documents should be retained for a longer period, however, if required by local regulations. No records will be destroyed without the written consent of the sponsor, if applicable. It is the responsibility of the sponsor to inform the investigator when these documents no longer need to be retained.

10.5.1 SOURCE DATA

Source data is all information, original records of clinical findings, observations, or other activities in a clinical trial necessary for the reconstruction and evaluation of the trial. Source data are contained in source documents. Examples of these original documents and data records include hospital records, clinical and office charts, laboratory notes, memoranda, subject diaries or evaluation checklists, pharmacy dispensing records, recorded data from automated instruments, copies or transcriptions certified after verification as being accurate and complete, microfiches, photographic negatives, microfilm or magnetic media, x-rays, subject files, and records kept at the pharmacy, at the laboratories, and at medico-technical departments involved in the clinical trial.

10.5.2 CASE REPORT FORMS

The study case report form (CRF) is the primary data collection instrument for the study. All data requested on the CRF must be recorded. All entries will be entered into an electronic data capture system (e-CRF). The Principal Investigator is responsible for assuring that the data entered into e-CRF is complete, accurate, and that entry and updates are performed in a timely manner.

10.5.3 CONFIDENTIALITY

The investigator must ensure the anonymity of the patients; patients must not be identified by names in any documents submitted to the sponsor. Signed informed consent forms and patient enrollment log must be kept strictly confidential to enable patient identification at the site. Information about study subjects will be kept confidential and managed according to the requirements of the Health Insurance Portability and Accountability Act of 1996 (HIPAA). Those regulations require a signed subject authorization informing the subject of the following:

- what protected health information (PHI) will be collected from subjects in this study;
- who will have access to that information and why;
- who will use or disclose that information; and
- the rights of a research subject to revoke their authorization for the use of their PHI.

If a subject revokes authorization to collect or use PHI, the investigator, by regulation, retains the ability to use all information collected prior to the revocation of subject authorization. For subjects that have revoked authorization to collect or use PHI, attempts should be made to obtain permission to collect at least vital status (i.e., that the subject is alive) at the end of their scheduled study period.

12 APPENDIX A

APPENDIX A: APACHE II Score Worksheet

[figure not shown]
A large black rectangular redaction box covers the majority of the page content below the header and logo.

13 APPENDIX B

APPENDIX B: SOFA score Worksheet

14 APPENDIX C

Berlin Definition of ARDS

Category	Criteria
Timing	Within 1 week of a known clinical insult or new or worsening respiratory symptoms
Chest Imaging (CT scan or X-Ray)	Bilateral opacities—not fully explained by effusions, lobar/lung collapse, or nodules
Origin of Edema	Respiratory failure not fully explained by cardiac failure or fluid overload. Need objective assessment (e.g., echocardiography) to exclude hydrostatic edema if no risk factor present
Severity based on Oxygenation ^a	Mild: $200 \text{ mm Hg} < \text{PaO}_2/\text{FIO}_2 \leq 300 \text{ mm Hg}$ with PEEP or CPAP $\geq 5 \text{ cm H}_2\text{O}$
	Moderate: $100 \text{ mm Hg} < \text{PaO}_2/\text{FIO}_2 \leq 200 \text{ mm Hg}$ with PEEP $\geq 5 \text{ cm H}_2\text{O}$
	Severe: $\text{PaO}_2/\text{FIO}_2 \leq 100 \text{ mm Hg}$ with PEEP $\geq 5 \text{ cm H}_2\text{O}$

a If altitude is higher than 1000 m, the correction factor should be calculated as follows: $[\text{PaO}_2/\text{FIO}_2 \text{ (barometric pressure/ 760)}]$

2019 ATS/IDSA criteria for severe pneumonia⁶

(Validated definition includes either one major criterion OR three or more minor criteria)

Category	Criteria
Major (1 needed)	Septic shock with need for vasopressors Respiratory failure requiring mechanical ventilation
Minor (≥ 3 needed if no major criteria met)	Respiratory rate ≥ 30 breaths/min $\text{PaO}_2/\text{FIO}_2$ ratio ≤ 250 Multilobar infiltrates Confusion/disorientation Uremia (blood urea nitrogen level $\geq 20 \text{ mg/dl}$) Leukopenia* (white blood cell count $< 4,000 \text{ cells}/\mu\text{l}$) Thrombocytopenia (platelet count $< 100,000/\mu\text{l}$) Hypothermia (core temperature $< 36^\circ\text{C}$) Hypotension requiring aggressive fluid resuscitation

*Due to infection alone (i.e., not chemotherapy induced).

15 APPENDIX D

WHO Ordinal Score

The World Health Organization has endorsed the use of an ordinal scale as an outcome measure in clinical trials to capture the trajectory of patients' clinical progression and of healthcare resource use.⁵¹

Score	Descriptor
1	Discharged (alive)
2	Hospital admission, not requiring supplemental oxygen, no longer requiring medical care (hospitalisation extended for infection control or other nonmedical reasons e.g. social care. Sometimes documented as "medically fit for discharge" or "medically stable for discharge")
3	Hospital admission, not requiring supplemental oxygen, but requiring ongoing medical care
4	Hospital admission, requiring supplemental oxygen (by face mask or nasal prongs)
5	Hospital admission, requiring high flow nasal oxygen, continuous positive airways pressure or non-invasive ventilation
6	Hospital admission, requiring invasive mechanical ventilation or extracorporeal membrane oxygenation (ECMO)
7	Death

16.1 STUDY DESIGN

16.1.1 SCHEMA

* If not discharged from the ICU

** Day 28 or last day of hospital, which ever comes first.

16.2 OVERALL STUDY DESIGN

This is a biospecimen and clinical data collection protocol in patients diagnosed with ARDS.

The design of the study stems from the treatment schedule described in the DC30-1A protocol.

16.3 SCHEDULE OF ACTIVITIES

Procedures	Study Visit 1/ Screening Visit ^j	Study Visit 2/ Day 1	Study Visit 3/ Day 2	Study Visit 4/ Day 3	Study Visit 5/ Day 4-6 ^f	Study Visit 6/ Day 28 ^g
Informed consent	X					
Demographics	X					
Medical history	X					
Concomitant Medications	X	X	X	X	X	X
Clinical End-point Assessment ^a		X	X	X	X	X
Research Blood Collection ^b	X	X	X	X	X ^e	X ^f
Exploratory BAL ^c	X				X ^e	
APACHE II score ^d	X					
CBC with differential ^h	X	X	X	X	X ^e	
Serum chemistry ^{h,i}	X	X	X	X	X ^e	
CRP, ferritin, D-Dimer	X	X	X	X	X ^e	
PT/INR, PTT ^h	X	X	X	X	X ^e	
Chest X-Ray or CT Scan	X				X ^e	X

a Clinical End-Point Assessments include: Survival (Y/N), On mechanical ventilation (Y/N), In ICU (Y/N), In Hospital (Y/N), Use of anti-coagulation (drug, dose, intent: prophylaxis vs therapeutic), WHO Ordinal Score. If patient is in ICU then the following assessment will be completed: Sequential Organ Failure Assessment (SOFA), PaO₂/FiO₂, ventilation variables (See Section 6 for details), recording of vasoactive drugs and renal support, recording of supportive interventions that can impact clinical end-points (i.e., use of prone ventilation, use of paralytics, use of pulmonary vasodilators, use of corticosteroids, use of oral decontamination and raising the head of the patient to at least 30° to prevent ventilator-associated pneumonia)

b See Laboratory Manual for details of sample collection for exploratory assays.

c If not possible, use tracheal aspirates.

d See [Appendix A](#) for APACHE II score system.

e To be done only once during this period

f If still in ICU

g Day 28 or last day of hospital, whichever comes first.

h If performed as Standard of Care

i Serum Chemistry includes Glucose, Ca, Mg, Phos, ALP, Albumin, Total Protein, Total Bilirubin, K, Na, Cl, HCO₃, BUN, Cr, ALT, AST, LDH, Amylase

16.4 STUDY PROCEDURES

This section explains the clinical and laboratory tests that will be performed in each study visit. See Section 16.3 for the study visit schedule.

16.4.1 SCREENING

All inclusion and exclusion criteria will be reviewed by the Investigator or qualified designee at the Screening Visit to ensure that the subject qualifies for the study. All inclusion criteria must be met, and none of the exclusion criteria may apply. Subjects found ineligible during the review of inclusion/exclusion will not proceed through the remaining screening process.

- Informed consent
- Demographics, Medical History
- Concomitant medications
- Research blood collection: All protocol required research blood collection assessments must be conducted in accordance with the Laboratory Manual and the Schedule of Activities. Laboratory requisition forms must be completed, and samples must be clearly labeled with the subject number, protocol number, site number, and visit date. Details for the preparation and shipment of samples will be provided by the laboratory and are detailed in the Laboratory Manual.
- Exploratory Bronchoalveolar lavage: See Laboratory Manual for more details. Should be done per 'institute's standards of operations. If BAL can not be performed then tracheal aspirate.
- Clinical End-point Assessment includes: Survival (Y/N), On mechanical ventilation (Y/N), In ICU (Y/N), In Hospital (Y/N), Use of anti-coagulation (drug, dose, intent: prophylaxis vs therapeutic), WHO Ordinal Score (See Appendix D for scale). If patient is in ICU then the following assessment will be completed: Sequential Organ Failure Assessment (SOFA, See [Appendix B](#) for template form), PaO₂/FiO₂, following ventilation parameters (as applicable): type of ventilation (CPAP, BiPAP, or intubation)/ ventilation rate/ pulse/ tidal volume/ positive end-expiratory pressure (PEEP), recording of vasoactive drugs and renal support, recording of supportive interventions that can impact clinical end-points (use of prone ventilation, use of paralytics, use of pulmonary vasodilators, use of corticosteroids, use of oral decontamination and raising the head of the patient to at least 30° to prevent ventilator-associated pneumonia).
- CBC with differential: Only if performed as Standard of Care.
- Serum chemistry: Only if performed as Standard of Care. Chemistry includes: Glucose, Ca, Mg, Phos, ALP, Albumin, Total Protein, Total Bilirubin, K, Na, Cl, HCO₃, BUN, Cr, ALT, AST, LDH, Amylase.
- CRP, ferritin, D-Dimer:
- PT/INR, PTT: If performed as Standard of Care.
- Chest Imaging: CT scan (preferred) or Chest X-Ray.

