- b Clinical End-Point Assessments include: Survival (Y/N), On mechanical ventilation (Y/N), In ICU (Y/N), In Hospital (Y/N), Use of anticoagulation (drug, dose, intent: prophylaxis vs therapeutic), WHO Ordinal Score. Following parameters to be collected only if patient is still in ICU: Sequential Organ Failure Assessment (SOFA), $\text{PaO}_2/\text{FiO}_2$, ventilation variables (See Section 6 for details), recording of vasoactive drugs and renal support, recording of supportive interventions that can impact clinical endpoints (i.e., use of prone ventilation, use of paralytics, use of pulmonary vasodilators, use of corticosteroids, use of oral decontamination and raising the head of the patient to at least 30° to prevent ventilator-associated pneumonia).
- c Vital signs include core temperature, mean arterial pressure (mmHg), pulse (beats/min), respiratory rate (breaths/min).
- d Samples should be taken in the morning between 04:00 and 10:00 using the values closest to 10:00.
- e Serum Chemistry includes Glucose, Ca, Mg, Phos, ALP, Albumin, Total Protein, Total Bilirubin, K, Na, Cl, HCO₃, BUN, Cr, ALT, AST, LDH, Amylase.
- f Only if there is clinical suspicion for COVID-19.
- g Blood or urine test, only in women of childbearing potential.
- h See Laboratory Manual for details of sample collection for exploratory assays.
- i See [Appendix A](#) for APACHE II score system.
- j Patient should continue to have respiratory failure as defined in Section 5.1 and moderate/severe ARDS status at least for 24 hours prior to signing consent. Screen visit and Day 0 infusion can be on the same day.
- k Assessments below should be done once a day unless stated otherwise.
- l If patient is discharged from the hospital these assessments can be omitted.
- m These assessments will be done on the day the patient leaves the administering unit or on Day 28, whichever comes earlier.
- n In-person or telemedicine. Omit Research Blood collection if telemedicine.
- o Optional based on PI discretion. If not possible, use tracheal aspirates for intubated patients and induced (preferred) or expectorated sputum for patients who are not intubated.
- p At least one time only during this period
- q If possible, CT scan is preferred.
- r Collection is done one-time pre-infusion and one-time post-infusion. See Laboratory Manual for details (for Research blood collections).
- s Should be done only if patient is in the hospital and procedure is Standard of Care as per PI discretion.

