- Research blood collection: All protocol required research blood collection assessments must be conducted in accordance with Laboratory Manual, and the Schedule of Activities. Laboratory requisition forms must be completed, and samples must be clearly labelled with the subject number, protocol number, site number, and visit date. Details for the preparation and shipment of samples will be provided by the laboratory and are detailed in the Laboratory Manual. Reference ranges for all safety parameters will be provided to the site by the laboratory responsible for the assessments.
- Exploratory Bronchoalveolar lavage, Tracheal Aspirate or sputum (induced or expectorated): Optional based on PI's discretion. See Schedule of Activities (Section 1)

and Laboratory Manual for more details. Should be done per institute's standards of operations (alternatively it can be done on Day 0 before infusion)

- Chest Imaging: CT scan or Chest X-Ray (alternatively it can be done on Day 0 before infusion)
- AE review and evaluation: AE collection starts after consent is signed.
- APACHE II Score: See [Appendix A](#) for APACHE II score.
- Clinical End-point Assessment includes: Survival (Y/N), On mechanical ventilation (Y/N), In ICU (Y/N), In Hospital (Y/N), Use of anti-coagulation (drug, dose, intent: prophylaxis vs therapeutic), WHO Ordinal Score (See Appendix D for scale). If patient is in ICU then the following assessment will be completed: Sequential Organ Failure Assessment (SOFA, See [Appendix B](#) for template form), PaO₂/FiO₂, following ventilation parameters (as applicable): type of ventilation (CPAP, BiPAP, or intubation)/ ventilation rate/ pulse/ tidal volume/ positive end-expiratory pressure (PEEP), recording of vasoactive drugs and renal support, recording of supportive interventions that can impact clinical endpoints (use of prone ventilation, use of paralytics, use of pulmonary vasodilators, use of corticosteroids, use of oral decontamination and raising the head of the patient to at least 30° to prevent ventilator-associated pneumonia).

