- Urinalysis: Samples should be taken in the morning between 04:00 and 10:00 using the values closest to 10:00. (mandatory for Arm 1, only if done as part of standard of care for Arm 2)
- Research blood collection: At least once between Day 3 and Day 6. All protocol required research blood collection assessments must be conducted in accordance with Laboratory Manual.
- Exploratory Bronchoalveolar lavage: **Should be done at least once during this period if it was performed prior to administration of cells.** If BAL is not performed then tracheal aspirate or sputum (induced or expectorated).
- Chest Imaging: CT scan or Chest X-Ray. Once between Days 1-6.
- AE review and evaluation
- PT/INR, PTT (Should be done at least once during this period, for patients in both Arms).

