6.5 SHORT-TERM FOLLOW-UP (DAY 14, 21 AND 28)

If patient is discharged from the hospital, Day 14 and 21 visits can be omitted. Day 28 visit can be the day of discharge from the hospital if it is earlier.

- Physical Exams: Only if patient is in the the administering unit, abbreviated, targeted physical examinations (i.e., assessments of the skin, respiratory, cardiovascular system, and abdomen (liver and spleen)), will be performed at time points specified in the Schedule of Activities (Section 1) and will be based on the subject's clinical status and what the clinic staff deem is appropriate.
- Concomitant medications
- Clinical End-point Assessment includes: Survival (Y/N), On mechanical ventilation (Y/N), In ICU (Y/N), In Hospital (Y/N), Use of anti-coagulation (drug, dose, intent: prophylaxis vs therapeutic), WHO Ordinal Score (See Appendix D for scale). If patient is in ICU then the following assessment will be completed: Sequential Organ Failure Assessment (SOFA), PaO₂/FiO₂, following ventilation parameters (as applicable): type of ventilation (CPAP, BiPAP, or intubation)/ ventilation rate/ pulse/ tidal volume/ positive end-expiratory pressure (PEEP), recording of vasoactive drugs and renal support, recording of supportive interventions that can impact clinical endpoints (use of prone ventilation, use of paralytics, use of pulmonary vasodilators, use of corticosteroids, use of oral decontamination and raising the head of the patient at least 30° to prevent ventilator-associated pneumonia)
- Vital Signs: include core temperature, mean arterial pressure (mmHg), pulse (beats/min), respiratory rate (breaths/min).
 - The same method for assessing temperature should be used at all visits for each individual subject, if possible.
- CBC with differential. Only if performed as Standard of Care.
- Serum chemistry. Only if performed as Standard of Care:

- Chemistry includes Glucose, Ca, Mg, Phos, ALP, Albumin, Total Protein, Total Bilirubin, K, Na, Cl, HCO₃, BUN, Cr, ALT, AST, LDH, Amylase.
- Chest Imaging: CT scan (preferred on Day 28) or Chest X-Ray. Only if performed as Standard of Care.
- AE review and evaluation
- Research blood collection: Only if patient is in the administering unit. All protocol required research blood collection assessments must be conducted in accordance with Laboratory Manual.

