16.4.3 DAYS 4-6

If the patient is still in ICU, the following assessments should be completed. There should be at least 12 hours between each assessment.

- Concomitant medications: Should be done daily.
- Clinical End-point Should be done daily. Assessment includes: Survival (Y/N), On mechanical ventilation (Y/N), In ICU (Y/N), In Hospital (Y/N), Use of anti-coagulation (drug, dose, intent: prophylaxis vs therapeutic), WHO Ordinal Score (See Appendix D for scale). If patient is in ICU then the following assessment will be completed: Sequential Organ Failure Assessment (SOFA), PaO₂/FiO₂, following ventilation parameters (as applicable): type of ventilation (CPAP, BiPAP, or intubation)/ ventilation rate/ pulse/ tidal volume/ positive end-expiratory pressure (PEEP), recording of vasoactive drugs and renal support, recording of supportive interventions that can impact clinical end-points (use of prone ventilation, use of paralytics, use of pulmonary vasodilators, use of corticosteroids, use of oral decontamination and raising the head of the patient to at least 30° to prevent ventilator-associated pneumonia)
- Research blood collection: Only once during this period. All protocol required research blood collection assessments must be conducted in accordance with Laboratory Manual.

- Exploratory Bronchoalveolar lavage: **This should be done only once during this period if not done on Days 1-3.** If BAL can not be performed, then tracheal aspirate.
- CBC with differential: Only once during this period and if performed as Standard of Care.
- Serum chemistry: Only once during this period and if performed as Standard of Care. Chemistry includes: Glucose, Ca, Mg, Phos, ALP, Albumin, Total Protein, Total Bilirubin, K, Na, Cl, HCO₃, BUN, Cr, ALT, AST, LDH, Amylase.
- CRP, ferritin, D-Dimer: Only once during this period.
- PT/INR, PTT: Only once and if performed as Standard of Care.
- Chest Imaging: CT scan (preferred) or Chest X-Ray, if performed as standard of care once during this period.

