16.4.4 DAY 28 (OR DAY OF DISCHARGE)

These assessments will be done on the day the patient leaves the hospital or on Day 28, whichever comes earlier.

- Concomitant medications
- Clinical End-point Assessment includes: Survival (Y/N), On mechanical ventilation (Y/N), In ICU (Y/N), In Hospital (Y/N), Use of anti-coagulation (drug, dose, intent: prophylaxis vs therapeutic), WHO Ordinal Score. If patient is in ICU then the following assessment will be completed: Sequential Organ Failure Assessment (SOFA), PaO₂/FiO₂, ventilation variables [type of ventilation (CPAP, BiPAP, or intubation), ventilation rate, pulse, tidal volume, positive end-expiratory pressure (PEEP)], recording of vasoactive drugs and renal support, recording of supportive interventions that can impact clinical end-points (use of prone ventilation, use of paralytics, use of pulmonary vasodilators, use of corticosteroids, use of oral decontamination and raising the head of the patient to at least 30° to prevent ventilator-associated pneumonia).
- Chest Imaging: CT scan (preferred) or Chest X-Ray.

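### Appendix E makes research lavage the default for untreated ARDS controls while the main protocol makes it optional for treated patients, so any airway-marker comparison sets samples obtained under different rules side by side; the Day-28 imaging rules also differ.

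*Combined protocol and SAP*

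**What the plan says.** **Who the controls are.** Section 16.2 describes Appendix E thus: "This is a biospecimen and clinical data collection protocol in patients diagnosed with ARDS". Its schedule contains no infusion. Section 16.5.1 compares treated patients with these parallel controls by a one-sided t-test on all continuous variables, and calls the analysis primarily descriptive.

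**Lavage in controls.** Section 16.4.1 lists it at screening, with the fallback "If BAL can not be performed then tracheal aspirate". Footnote c of the 16.3 schedule gives the same fallback. Section 16.4.2 lists one lavage on Days 1-3, at least 48 hours after the screening collection. Section 16.4.3 adds for Days 4-6: "This should be done only once during this period if not done on Days 1-3". The visible text gives no investigator option, does not tie the second lavage to a baseline lavage, and does not accept sputum.

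**Lavage in treated patients.** Footnote o of the Section 1 schedule says "Optional based on PI discretion", and 6.1 says "Optional based on PI's discretion". Section 6.3 says of the follow-up lavage: "Should be done at least once during this period if it was performed prior to administration of cells". Section 6.4 carries the same condition to Day 7. Tracheal aspirate or sputum is an accepted substitute.

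**Day-28 or discharge imaging.** For controls, 16.4.4 lists "CT scan (preferred) or Chest X-Ray" with no standard-of-care limit, and 16.3 adds none. For treated patients, 6.5 says "CT scan (preferred on Day 28) or Chest X-Ray. Only if performed as Standard of Care", and footnote s of the Section 1 schedule says the same in substance.

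**The concern.** Two things are at stake.

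**Participant burden.** Controls have ARDS and receive no study product. An invasive airway procedure done for research is their default, yet it is optional for patients who do receive the product. The visible documents give no reason. Appendix E limits other items to standard of care (blood count, chemistry, coagulation and, in 16.4.3, the Days 4-6 scan), so the authors had such wording to hand and did not use it for the lavage or the Day-28 scan.

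**Comparability.** A treated lavage sample exists only where an investigator chose to take it. A control sample exists wherever lavage could be done. If that choice depends on how sick the patient is, and the marker also depends on severity, the groups differ before any drug effect. A one-sided test is sensitive to such a shift in one direction and blind to it in the other. Accepting sputum in one group only may also change the mix of sample types.

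**Working it through.** The plan gives no figure to reproduce here. The check is a count of procedures and a conditional illustration of bias.

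**1. Lavage count, for a patient who stays in the unit**

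| | Controls (Appendix E) | Treated (main protocol) |
|---|---|---|
| Baseline | 1 by default (16.4.1) | 0 required; optional (footnote o, 6.1) |
| Follow-up | 1 by default, Days 1-3 or else 4-6 (16.4.2, 16.4.3) | only if a pre-infusion lavage was done (6.3, 6.4) |
| Substitute | tracheal aspirate | tracheal aspirate or sputum |
| Total | 1 + 1 = 2 | 0 required; at least 2 if the first is elected |

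The control total is an upper limit, because 16.4.2 and 16.4.3 drop assessments after ICU discharge.

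**2. Scans without a standard-of-care limit**

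- Treated: before first infusion, once in Days 1-6 (6.2, 6.3), and Day 7 (6.4): 1 + 1 + 1 = 3.
- Controls, procedure text: screening (16.4.1) and Day 28 or discharge (16.4.4): 1 + 1 = 2.
- Controls, 16.3 table: the same plus Days 4-6, which the table marks without the limit that 16.4.3 imposes: 2 + 1 = 3.

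At the Day-28 or discharge visit alone, the count is 1 for controls and 0 for treated patients.

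**3. Conflicts inside Appendix E**

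- The 16.3 table shows lavage at screening and Days 4-6 only; 16.4.2 also lists it on Days 1-3.
- The 16.3 table has no standard-of-care limit on Days 4-6 imaging; 16.4.3 has one.

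**4. What the difference in sampling could do**

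The one documented input is 24 treated ARDS patients (12 in Arm 1 plus 12 in the Arm 2 ARDS cohort). Everything else is assumed: 12 controls, a one-sided 5% level, no drug effect, lower marker values favourable, and an investigator judgement that correlates 0.7 with severity and decides who is lavaged. Let ρ be the correlation of severity with the log marker. If the fittest 12 of 24 are sampled and controls are unselected,

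shift = −0.7 × ρ × 0.77 SD,

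where 0.77 is the mean of the upper half of 24 standard normal values. For ρ = 0.3, 0.5 and 0.7 this gives −0.16, −0.27 and −0.38 SD. Simulation with 40,000 replicates per setting gives:

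| Who is lavaged | Rejection at ρ = 0.3 / 0.5 / 0.7 |
|---|---|
| Fittest 12 of 24 treated; controls unselected | 10% / 16% / 24% |
| Fittest 18 of 24 treated; controls unselected | 8% / 10% / 14% |
| Fittest 12 of 24 treated; fittest 12 of 16 controls | 7% / 9% / 13% |
| Fittest 18 of 24 treated; fittest 12 of 16 controls | 5% / 5% / 6% |
| Discretion unrelated to severity; controls unselected | 5% / 5% / 5% |
| Sickest 12 of 24 treated; controls unselected | 2% / 1% / 1% (shift +0.16 / +0.27 / +0.38 SD) |

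The result runs from well above nominal to well below it, depending on inputs that the documents do not give. The table shows that selection can matter, not how much it does.

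**The case against.** **Controls are not worse off overall.** A reader might infer that controls carry more research risk in total. The documents do not support that. Only treated patients receive the investigational cells, and they have 3 scans without a standard-of-care limit against 2 or 3 for controls. A plain X-ray also satisfies 16.4.4. The burden argument stands for the lavage and, more weakly, for the single Day-28 or discharge scan.

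**The bias has no established direction.** A reader might infer that the comparison leans toward Descartes-30. That requires fitter treated patients to be the ones lavaged. Intubated, sicker patients may be easier to lavage, and the sign then reverses. Control sampling is also filtered by whether lavage can be done, which shrinks the difference. This objection stands in full against any directional figure.

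**No airway or imaging endpoint is visible.** Sections 16.5.2 and 16.5.3 are largely redacted, and 9.3 lists no imaging endpoint. A biased comparison of Day-28 images is therefore not something the documents show. An airway-marker comparison is plausible, since lavage is collected in both groups and 16.5.1 covers all continuous variables, but it has to be stated conditionally.

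**The imaging rules are not different throughout.** On the 16.3 table, Days 4-6 imaging is close to the treated rule for Days 1-6. Only the text of 16.4.3 makes it differ.

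**Release wording may exist elsewhere.** The Laboratory Manual is not supplied and the page before 16.1 is not available. Lavage is also to follow institutional standards in both groups. The visible schedule and procedure text would still need to agree.

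**Biospecimens are the appendix's purpose.** True, and a reasoned justification for default lavage might rest on it. None is given.

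**Conclusion.** The point holds in a limited form. By default, up to 2 research lavages are scheduled per control against 0 required per treated patient. The follow-up condition and the accepted substitutes differ as well. If lavage markers enter the 16.5.1 comparison, investigator-selected treated samples would face default control samples. The resulting bias could favour Descartes-30, work against it or be nil, and the documents do not allow it to be sized. The Day-28 or discharge scan also follows different rules in the two groups, but this is a mismatch at one visit and not a net excess of imaging for controls.

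The conclusion rests on the visible schedules and procedure text, and on reading the appendix's wording as a default rather than a strict mandate. It is worth acting on because the correction is cheap and spares untreated patients a default invasive research procedure.

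**What to change.** 1. **One lavage rule for both groups.** Reconcile 16.3 (footnote c) and 16.4.1-16.4.3 with footnote o, 6.1, 6.3 and 6.4 on whether lavage is optional, whether the follow-up depends on a baseline sample, and which substitutes are accepted. Unless the sponsor justifies default lavage in controls, the low-burden way is to make it optional there too.
2. **Reconcile Appendix E with itself.** Bring the 16.3 table into line with 16.4.2 on Days 1-3 lavage and with 16.4.3 on the Days 4-6 imaging limit.
3. **Reconcile Day-28 or discharge imaging** between 6.5 and 16.4.4, and in both schedules.
4. **Record** in both groups the type of airway sample and, where lavage was not done, the reason.
5. **Adjust** any airway-marker comparison for PaO2/FiO2 and ventilation status at sampling. Both groups already collect ventilation status, and PaO2/FiO2 while in ICU. State that residual selection remains, because the study is open-label and a shared discretionary rule can still be applied differently to treated and control patients.

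The cost is wording in Appendix E and small e-CRF additions. The downside is somewhat fewer control lavage samples and Day-28 images.
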